5.2.2 Unscheduled Visits

All attempts should be made to keep patients on the study schedule. Unscheduled visits may be necessary to repeat testing following abnormal laboratory results, for follow-up of AEs, or for any other reason, as warranted.

If patient presents on POD 4 and have not epithelialized, patient will be brought in on POD 5 to re-assess epithelialization and remove bandage contact lens (BCL). This will be collected as an unscheduled visit.

5.2.3 Adverse Event Information Collection

The investigator (or designee) will record all AEs that occur during the study. The definition of an AE and SAE, and information on the determination of severity and relationship to treatment are provided in Section 6.

5.3 **Rescue Criteria**

If the investigator determines either eye requires additional post-operative treatment, topical prednisolone acetate 1% therapy may be added to the DEXTENZA eye or increased dosing frequency may be offered to eyes receiving topical prednisolone acetate 1%. The investigator may also prescribe either or both topical cyclosporine 0.05% or topical cyclosporine 0.09%.

6. **SAFETY DEFINITIONS, REPORTING, AND MONITORING**

6.1 **Definitions**

6.1.1 **Adverse Event**

An AE is any untoward medical occurrence in a patient administered a study drug which may or may not have a causal relationship with the study drug. Therefore, an AE is any unfavorable and unintended sign (including abnormal laboratory finding), symptom, or disease which is temporally associated with the use of a study drug, whether or not considered related to the study drug.

An AE also includes any worsening (i.e. any clinically significant change in frequency and/or intensity) of a pre-existing condition that is temporally associated with the use of the study drug.

6.1.2 **Serious Adverse Event**

A SAE is any untoward medical occurrence that at any dose:

- Results in **death** – includes all deaths, even those that appear to be completely unrelated to study drug (e.g. a car accident in which a patient is a passenger).
- Is **life-threatening** – in the view of the investigator, the patient is at immediate risk of death at the time of the event. This does not include an AE that had it occurred in a more severe form, might have caused death.
- Requires in-patient **hospitalization** or prolongation of existing hospitalization. In-patient hospitalization is defined as admission to a hospital or an emergency room for longer than 24 hours. Prolongation of existing hospitalization is defined as a hospital stay that is longer than was originally anticipated for the event, or is prolonged due to the development of a new AE as determined by the investigator or treating physician.
- Results in persistent or significant **disability/incapacity** (substantial disruption of one's ability to conduct normal life functions).
- Is a **congenital anomaly/birth defect**
- Is an **important medical event** – Important medical events may not be immediately life-threatening or result in death or hospitalization, but may jeopardize the patient or may require intervention to prevent 1 of the other serious outcomes listed above (e.g., intensive treatment in an

emergency room or at home for allergic bronchospasm; blood dyscrasias or convulsions that do not result in hospitalization; or development of drug dependency or drug abuse). Any malignancy (other than basal cell skin cancers) would be considered a medically important event.

6.2 Recording and Reporting Adverse Events

All AEs and SAEs will be recorded only if they are medically relevant.

All SAEs, regardless of assessment of causal relationship to study insert will be reported to Ocular Therapeutix.

To report an SAE, Ocular Therapeutix will be contacted at the following:

[contact]
SAE [contact]

The investigator will promptly report to the IRB all unanticipated problems involving risks to patients. This includes death from any cause and all SAEs related to the use of the study insert. All SAEs will be reported to the IRB, regardless of assessed causality.

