2.3 Safety Endpoints

To determine through Month 3 (+/- 4 days):

- Incidence of increased IOP >10 mmHg above baseline at all timepoints
- Occurrence of adverse events at all timepoints

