5. STUDY SCHEDULE OF EVENTS AND VISIT DESCRIPTIONS

5.1 Schedule of Events

Study assessments and procedures are presented by visit in Table 1.

Table 1 Schedule of Events

Study Procedure	Screening/ Baseline	Surgical Visit Day 0	Day 3	Day 4	Day 14	Day 28	3 MTH post-op	Early Terminat ion
Visit	VISIT 1	VISIT 2	VISIT 3	VISIT 4	Phone call 1	VISIT 5	VISIT 6	
Windows for Visits	(Day -30 to -1)				(+/- 2 days)	(+/- 3 days)	(+/- 3 days)	
Inclusion/Exclusion	X							
Informed Consent	X							
Demographics	X							
Medical History and Concurrent Illnesses	X							
Concomitant Medications	X	X	X	X		X	X	
Randomization	X							
Confirm Treatment Group		X						
Uncorrected Distance VA testing	X					X	X	
Manifest Refraction	X					X	X	
BCVA (ETDRS at 4m)	X					X	X	
Corneal Haze (via AS-OCT)	X					X	X	
Intraocular Pressure	X		X	X		X	X	
Corneal Staining	X		X	X		X	X	
Slit Lamp Exam	X		X	X		X	X	
Ophthalmic Examination (dilated fundus exam)	X							
Ocular Pain Assessment	X		X	X	X	X		
SPEED Questionnaire	X					X		
COMTOL Survey						X		
Record any surgical complications		X						
Subject reported AEs prior to or after surgery	X	X	X	X	X	X	X	
Intracanalicular dexamethasone insert*		X						
Prescribe post-operative topical therapy regimen**		X						
Insert Visualization			X	X		X	X	

*Eye Randomized to Group A

**Specific for each eye based on Group A or B

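### Section 6.2 lets an undefined relevance test decide which adverse events are recorded, against Section 5.2.3, which requires all of them

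*Protocol*

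**What the plan says.** The protocol gives two recording rules. Section 5.2.3 says: "The investigator (or designee) will record all AEs that occur during the study". Section 6.2 says: "All AEs and SAEs will be recorded only if they are medically relevant".

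Section 6.1.1 sets the scope: "An AE is any untoward medical occurrence in a patient administered a study drug which may or may not have a causal relationship". It goes on to include unfavourable signs and symptoms and the worsening of existing conditions. Relevance is not part of the definition.

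Section 5.2.3 also tells the reader that "information on the determination of severity and relationship to treatment are provided in Section 6".

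For serious events, 6.2 adds two reporting duties without any filter: "All SAEs, regardless of assessment of causal relationship to study insert will be reported to Ocular Therapeutix", and "All SAEs will be reported to the IRB, regardless of assessed causality".

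The endpoint that depends on these rules is in Section 2.3: "Occurrence of adverse events at all timepoints". Table 1 in Section 5.1 supplies its data through the row "Subject reported AEs prior to or after surgery", marked at baseline, Day 0, Day 3, Day 4, the Day 14 phone call, Day 28 and Month 3.

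**The concern.** One section orders complete capture and another makes capture conditional on a judgement that has no criterion. Site staff who follow 6.2 will discard some of the answers that Table 1 has them collect, and the safety count will then depend on an unstated personal threshold.

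The loss occurs at data capture. An analysis plan can classify or tabulate recorded events in any way it likes, but it cannot restore a subject-reported event that was never written down.

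The design adds a second risk. Section 3.1 describes the study as open-label, and each patient has a different treatment in each eye. Whoever judges relevance may know which eye received the insert, so the filter could act differently on the two eyes. This is possible; nothing in the protocol shows that it will happen. Section 5.2.1 has a masked examiner for slit lamp and corneal staining, which reduces the risk for signs found at those examinations. It does not reduce it for symptoms that patients report, such as those from the Day 14 call.

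**Working it through.** The main point is textual, so the rules are set against each other first.

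1. **Non-serious events.** Take an event that meets 6.1.1 but that someone considers not medically relevant. Under 5.2.3 it is recorded; under 6.2 it is not. The two rules conflict directly.
2. **The criterion.** The term occurs only in 6.2 and is not defined. The nearest expression, the important medical event in 6.1.2, is a criterion for seriousness. Borrowed as the filter, it would remove nearly all non-serious events. Section 5.2.3 points to Section 6 for severity and relationship, but 6.1.1, 6.1.2 and 6.2 contain only definitions and reporting duties. Nothing there anchors the filter.
3. **Serious events.** Section 6.2 makes recording conditional and reporting unconditional. Section 6.1.2 counts every death as serious, even one plainly unrelated to the study drug. Such a death must be reported, yet it could fail an undefined relevance test for recording. This is a tension rather than a strict contradiction, and the reporting duty still stands.
4. **The endpoint.** Section 2.3 counts adverse events without a relevance limit, so recording under 6.2 does not deliver the stated endpoint.

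**Size of one omission.** The synopsis gives 20 patients and 40 eyes, with one eye of each patient in each group, so 20 eyes per group.

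- If the omitted event is the only ocular event in its eye, the group's incidence falls by 1/20 = 0.05, or 5 percentage points.
- If the eye already has a recorded ocular event, the change is 0.
- A systemic event cannot be assigned to an eye.

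The protocol gives no event rate, so the number of omissions cannot be estimated.

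**IOP note.** The synopsis counts a rise of at least 10 mmHg over baseline; Section 2.3 counts a rise strictly above 10. The two differ only for an eye whose largest rise is exactly 10. The protocol gives no distribution of IOP change, so the following rests on assumption: changes are normal with mean 0, 2 or 4 and SD 3, 4 or 5 mmHg, read in whole mmHg. The expected difference at one assessment is

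20 × [P(change ≥ 9.5) − P(change ≥ 10.5)].

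- Smallest (mean 0, SD 3): 20 × (0.00077 − 0.00023) = 0.011 eyes, or about 0.05 percentage points.
- Largest (mean 4, SD 5): the standardised cut-offs are (9.5 − 4)/5 = 1.1 and (10.5 − 4)/5 = 1.3, with tail probabilities 0.1357 and 0.0968. Then 20 × (0.1357 − 0.0968) = 0.78 eyes, or 3.9 percentage points.

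These figures are per assessment. Table 1 has four post-operative IOP readings (Day 3, Day 4, Day 28, Month 3). If the endpoint counts an eye with a rise at any of them, and the readings are taken as independent, the largest case becomes 20 × (0.9032⁴ − 0.8643⁴) = 20 × (0.665 − 0.558) = about 2.1 eyes. Readings on one eye are usually positively correlated, which would tend to lower this figure.

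**The case against.** The best defence is that little is lost in practice. All serious events still go to the manufacturer and the IRB, and few of them would be judged irrelevant. IOP, staining, slit lamp findings, haze, pain and concomitant medications are collected on schedule whatever the filter does. The primary endpoint, the COMTOL survey, is untouched. Section 5.2.3 names the investigator or designee as the recorder, so it is reasonably clear who would apply the test. The baseline contact precedes study drug, so under 6.1.1 at most six of the seven contacts marked in Table 1 can yield an adverse event. The IOP threshold is a separate matter.

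Much of this is fair. The serious-event part is the weaker part, the recorder is identified by implication, and the IOP difference is minor and does not support the main point. The contact count is also fair on the 6.1.1 definition, although the Table 1 row covers events before surgery as well.

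The defence does not remove the contradiction. Scheduled measurements preserve the signs and scores they cover, but they do not restore a non-serious symptom that a patient reported and nobody recorded. The person applying the test is implied, but the criterion is still missing.

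**Conclusion.** Section 6.2 is wrong as written. It contradicts 5.2.3, applies a filter that the definition in 6.1.1 does not contain, and would under-count a named safety endpoint in a way that cannot be repaired later. The practical effect is mainly on non-serious events. Each eye whose only ocular event is omitted costs its group 5 percentage points, given 20 eyes per group with all 20 patients analysed. The total loss cannot be estimated from the protocol, and a difference between the two eyes in how the filter acts remains a possibility only.

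The contradiction rests on the text alone and needs no assumption. The IOP figures do rest on assumed distributions: 0.01 to 0.78 eyes in 20 per assessment, and up to about 2.1 eyes over four independent readings. That point is secondary.

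**What to change.** Replace the sentence in 6.2 with, for example: *Every AE and SAE is recorded, by eye where it is ocular, whatever its perceived relevance or cause.* This brings 6.2 into line with 5.2.3, 6.1.1 and 2.3. If medical relevance is of interest, record it as an attribute of each event, so that it can be used in tabulation without deleting data. Recording by eye is an addition beyond the contradiction itself, but a comparison of the two groups needs it.

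Either add the severity and relationship criteria to Section 6 or remove the reference to them in 5.2.3. Separately, reconcile the IOP-rise definitions in the synopsis and Section 2.3 to one wording before data are analysed.

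The cost is one sentence, one cross-reference and one endpoint wording. Sites will make slightly more entries, and reported incidences may be higher. The changes concern recording and endpoint definition only.

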7. STUDY VARIABLES

7.1 Demographic and Baseline Characteristics

Baseline characteristics will include standard demography (e.g. age, race, weight, height, etc.), disease characteristics including medical history, and medication history for each patient.

8. ETHICAL AND REGULATORY CONSIDERATIONS

8.1 Good Clinical Practice Statement

It is the responsibility of the investigator(s) to ensure that this clinical study will be conducted in accordance with the ethical principles that have their origin in the Declaration of Helsinki, and that are consistent with the ICH guidelines for Good Clinical Practice (GCP) and applicable regulatory requirements.

8.2 Informed Consent

The principles of informed consent are described in ICH Guidelines for GCP.

Ocular Therapeutix will have the right to review and comment on the informed consent form.

It is the responsibility of the investigator or designee (if acceptable by local regulations) to obtain written informed consent from each patient prior to his/her participation in the study and after the aims, methods, objectives, and

potential hazards of the study have been explained to the patient in language that he/she can understand. The ICF will be signed and dated by the patient and by the investigator or authorized designee who reviewed the ICF with the patient.

Patients who can write but cannot read will have the ICF read to them before signing and dating the ICF.

Patients who can understand but who can neither write nor read will have the ICF read to them in presence of an impartial witness, who will sign and date the ICF to confirm that informed consent was given.

The original ICF will be retained by the investigator as part of the patient's study record, and a copy of the signed ICF will be given to the patient.

If new safety information results in significant changes in the risk/benefit assessment, the ICF will be reviewed and updated appropriately. All study patients will be informed of the new information and provide their written consent if they wish to continue in the study. The original signed revised ICF will be maintained in the patient's study record and a copy will be given to the patient.

8.3 Patient Confidentiality and Data Protection

The investigator will take all appropriate measures to ensure that the anonymity of each study patient will be maintained.

The patient's and investigator's personal data will be treated in compliance with all applicable laws and regulations.

8.4 Institutional Review Board

An appropriately constituted IRB, as described in ICH Guidelines for GCP, will review and approve:

- The protocol, ICF, and any other materials to be provided to the patients (e.g. advertising) before any patient may be enrolled in the study
- Any amendment or modification to the study protocol or ICF before implementation, unless the change is necessary to eliminate an immediate hazard to the patients, in which case the IRB will be informed as soon as possible

Ongoing studies will be reviewed by the IRB/EC on an annual basis or at intervals appropriate to the degree of risk.

In addition, the IRB will be informed of any event likely to affect the safety of patients or the continued conduct of the clinical study.

A copy of the IRB approval letter will be sent to Ocular Therapeutix prior to shipment of drug insert supplies to the investigator. The approval letter will include the study title, the documents reviewed, and the date of the review.

Records of the IRB review and approval of all study documents (including approval of ongoing studies) will be kept on file by the investigator.

REFERENCES

1. DEXTENZA [PACKAGE INSERT]. BEDFORD, MA: OCULAR THERAPEUTIX, INC; 2019.
